#### **10.6 Protocol Exceptions and Deviations**

No prospective entry criteria protocol deviations are allowed; all subjects must meet all eligibility criteria in order to participate in the study.

Protocol waivers for eligibility will not be granted by the Sponsor under any circumstances. If, during the course of a subject's post-randomization participation in the trial it is discovered that the subject did not meet all eligibility criteria, s/he will be discontinued, unless the discontinuation presents an unacceptable medical risk. The justification to allow the subject to continue in the trial will be made by the Sponsor, with medical input from the Investigator, and will be documented. If allowed to remain in the trial, this will be reported as a major protocol deviation and not a waiver. All follow-up safety assessments must be completed and documented as outlined in the protocol. The Investigator must report any protocol deviation to the Sponsor and, if required, to the IRB/EC in accordance with local regulations, within reasonable time.

#### **10.7 Termination of the Study**

The Sponsor reserves the right to discontinue the study at any time for any reason. Such reasons may be any of, but not limited to, the following:

- Occurrence of AEs unknown to date in respect of their nature, severity, and duration or the unexpected incidence of known AEs
- Medical or ethical reasons affecting the continued performance of the study
- Sponsor business reasons

Regulatory Authorities also have the right to terminate the conduct of the study in their region for any reason.

#### **10.8 Publication**

All publication rights are delineated in the Clinical Study Agreement and/or other separate agreements with the Investigator and/or Institution, as applicable.

## APPENDIX A SCHEDULE OF EVENTS AND ASSESSMENTS

Procedure	Visit Number	Screening Period	Treatment Period					Follow-Up
			Visit 1 a Baseline (1)	Visit 2 a Week 2 (15)	Visit 3 a Week 4 (29)	Visit 4 a Week 8 (57)	Visit 5 a (EOS/ET)	
Visit Week (Day)	Week -2 to -4 b							
Allowable visit window (# days)	NA	NA	±3	±3	±3	±3	±3	+7
Clinic (C) or Telephone (T) Visit	C	C	C	C	C	C	C	T
Informed consent	X							
Inclusion/exclusion criteria assessment	X	X d						
Medical history and demographics	X							
Alzheimer's disease history	X							
Physical examination	X							X
Vital signs (including height e and weight)	X	X	X	X	X	X	X	
ECG f	X	X		X				X
Clinical laboratory tests g	X	X		X				X
Pregnancy test h	X	X		X				X
PK sampling		X	X i	X				X
CMAI		X	X	X	X	X	X	
ZBI		X	X	X	X	X	X	
NPI-C (Agitation and Aggression Domains)	X j	X	X	X	X	X	X	
NPI-C (All Remaining Domains)		X						X
MMSE	X	X		X	X	X	X	
mADCS-CGIC		X	X	X	X	X	X	
KSS		X	X	X	X	X	X	
ADCS-ADL		X						X
MRI or CT k	X							
Psychosocial therapy	X							
Assessment of concomitant medications/treatments	X	X	X	X	X	X	X	X
Assessment of adverse events l	X	X	X	X	X	X	X	X
GCAS	X	X	X	X	X	X	X	X
Randomization		X						
Dispense study drug		X		X	X			
Study drug administration at the clinic m		X						
Study drug accountability				X	X	X		

Abbreviations and footnotes on [next page](#).

Abbreviations: AD=Alzheimer's Disease; ADCS-ADL=Alzheimer's Disease Cooperative Study-Activities of Daily Living Inventory; C=clinic visit; CMAI=Cohen-Mansfield Agitation Inventory; CT=computed tomography; ECG=electrocardiogram; EOS=end of study; ET=early termination; GCAS=Global Clinician Assessment of Suicidality; KSS=Karolinska Sleepiness Scale; MMSE=Mini-Mental State Examination; mADCS-CGIC=modified Alzheimer's Disease Cooperative Study – Clinical Global Impression of Change; MRI=magnetic resonance imaging; NA=not applicable; NPI-C=Neuropsychiatric Inventory-Clinician Rating Scale; PK=pharmacokinetic; ZBI=Zarit Burden Interview

- a. Study visits are designated by weeks and have a  $\pm 3$ -day window (Visits 2 through 5) or a +7-day window (Visit 6) calculated from the Baseline Visit (Day 1). Clinic visits may be split over multiple days within the specified windows, if necessary.
- b. The screening period must be at least 2 weeks long and no more than 4 weeks long.
- c. For subjects who discontinue prematurely from the study or who do not enroll in the open-label extension study, a follow-up safety assessment will be conducted by telephone call approximately 30 days after the last dose of study drug.
- d. NPI-C combined agitation and aggression domain score, ECG, and wash-out of prohibited medications are the only eligibility assessments required at both Screening and Baseline (Day 1). All other eligibility criteria are to be established during Screening.
- e. Height is assessed as part of the vital sign measurement only at the Screening Visit; weight will be assessed at every clinic visit as part of the vital sign measurements.
- f. 12-lead ECG to be completed in triplicate at screening and single read at subsequent visits. ECGs can be performed any time before blood sampling or at least 30 minutes after blood sampling during clinic visits.
- g. Urinalysis requirement not applicable to subjects who are unable to provide urine sample (e.g., incontinent subjects).
- h. A serum pregnancy test should be performed at the initial screening visit. A urine pregnancy test should be performed at Baseline (Day 1), Week 4, and Week 12 (EOS/ET) for female subjects of childbearing potential.
- i. Note: If collection at Week 2 does not occur, then collection should be attempted at Week 8.
- j. Only the agitation and aggression domain will be completed at the Screening Visit.
- k. MRI or CT must be obtained during or subsequent to diagnosis of probable AD, or during the screening period (prior to Baseline).
- l. Any untoward medical occurrence that occurs after signing the informed consent form (i.e., during the screening period) should be recorded as an adverse event, even if dosing has not begun.
- m. The first dose of study drug must be administered to the subject at the clinic only after all baseline assessments are performed, including the blood sampling for PK assessment. If any baseline assessments extend to an additional day, the first dose of study drug will be administered at completion of assessments on this day.

## **APPENDIX C PROHIBITED AND RESTRICTED CONCOMITANT MEDICATIONS**

*The following is an outline of the prohibitions and restrictions on concomitant medications. Any questions regarding prohibited and restricted concomitant medications should be discussed with the Medical Monitor or appropriate designee.*

Subjects who take prohibited concomitant medications during the trial will be discontinued, unless the discontinuation presents an unacceptable medical risk. The justification to allow the subject to continue in the trial will be made by the Sponsor with medical input from the Investigator, and will be documented. If allowed to remain in the trial, this will be reported as a major protocol deviation and not a waiver.

### **1. Antipsychotics:**

- All antipsychotics are prohibited and should be discontinued as appropriate 2 weeks or at least 5 half-lives (whichever is longer) prior to Baseline.

### **2. Serotonin antagonists:**

- Serotonin antagonists are prohibited and must have been discontinued at least 3 weeks prior to Baseline. This includes, but is not limited to: mianserin, nefazodone, cyproheptadine, and fluvoxamine.
- Trazodone is prohibited as a serotonin antagonist and also due to possible QT prolongation.

### **3. Anticholinergic medications:**

- Centrally acting anticholinergic medications are prohibited and should be tapered off and discontinued at least 2 weeks prior to Baseline. These include, but are not limited to diphenhydramine, benz tropine, biperiden, and trihexylphenidyl.
- Peripherally acting anticholinergic agents, such as tolterodine or oxybutynin, are allowed.

### **4. Antidepressants:**

- Use of antidepressant medications is restricted. The dose of these medications must be unchanged for at least 4 weeks prior to Baseline and should be expected to remain unchanged until the subject's final visit.
- Trazodone is prohibited as an antidepressant and also due to possible QT prolongation.
- See also the restrictions on antidepressants that can prolong the QT interval in #6 below. These antidepressants include citalopram, escitalopram, clomipramine, desipramine, imipramine, mirtazapine, and nortriptyline

## 5. Anxiolytics and sedative medications:

- Use of anxiolytic medications (including benzodiazepine) is restricted. The dose of these medications must be unchanged for at least 4 weeks prior to Baseline and should be expected to remain unchanged until the subject's final visit.
- Exception: lorazepam (a benzodiazepine) may be used as a rescue medication for the management of agitation and/or aggression per [Section 5.7.3](#). If lorazepam is not available, another intermediate-acting benzodiazepine may be used in the same way lorazepam may be used at doses equivalent to lorazepam doses.
- Use of sedative insomnia aids is permitted PRN with restrictions as noted in the list of prohibited and restricted medications.

## 6. Medications that can prolong QT interval

Medications that can prolong QT interval are prohibited or restricted as outlined below. These include, but are not limited to the following:

### *Prohibited for the duration of the study:*

- Antiarrhythmic drugs including: dronedarone, quinidine, procainamide, disopyramide, ajmaline, flecainide, propafenone, amiodarone, sotalol, d-sotalol, bretylium, ibutilide, dofetilide, amakalant, and semantilide
- Antimicrobial and antimalarial drugs; levofloxacin, moxifloxacin, erythromycin, clarithromycin, and pentamidine
- Methadone and cocaine

### *Prohibited at study entry but allowed in restricted situations after randomization*

- Use of ciprofloxacin and azithromycin is prohibited at Baseline. However, use of these drugs during the course of the study to treat a bacterial infection (e.g., urinary tract infection, respiratory infection), post-Baseline may be permitted at the discretion of the PI.

### *Restricted under certain conditions:*

- Citalopram and escitalopram are restricted to a maximum dose of 20 mg a day. If it is clinically appropriate, subjects on a higher dose of citalopram or escitalopram should be titrated down to 20 mg a day prior to Baseline.
- The medications listed are **ONLY** allowed if:
  - the subject has a baseline ECG with a QTcF <425 ms **OR**
  - the subject has a QTcF <450 ms at Baseline **AND** QRS duration  $\geq$ 120 ms (e.g., subjects with right bundle branch block [RBBB] or left bundle branch

block [LBBB], an intraventricular conduction disturbance [IVCD], or ventricular pacing)

Antimicrobials, antifungals, and antimalarials	Antidepressants	Others

• artenimol/piperaquine

• bedaquiline

• gemifloxacin

• norfloxacin

• ofloxacin

• quinine

• roxithromycin

	

• clomipramine

• desipramine

• imipramine

• mirtazapine

• nortriptyline

	

• felbamate

- The medications listed above are **not allowed** if a subject has a QTcF  $\geq 425$  ms and a QRS duration  $< 120$  ms at baseline.

## APPENDIX D LIST OF PROHIBITED CYP3A4 INHIBITORS AND INDUCERS

The information presented here is intended to provide guidance and does not constitute an exhaustive list of strong CYP3A4 inhibitors and inducers. Any questions should be discussed with the Medical Monitor or appropriate designee.

The metabolism of pimavanserin is affected by strong cytochrome P450 (CYP) 3A4 enzyme (CYP3A4) inhibitors, resulting in an increase in maximum plasma concentration ( $C_{max}$ ) and area under the plasma concentration-time curve (AUC) of approximately 3-fold. Strong inhibitors and inducers of CYP3A4 are to be stopped 1 week prior to the administration of study drug and are prohibited throughout the study. Moderate inhibitors and inducers of CYP3A4 are allowed but should be used with caution.

STRONG INDUCERS	Avasimibe Carbamazepine (Tegretol®) Phenobarbital (Luminal®, Solfoton®) Phenytoin (Dilantin®) Rifampin (Rifadin®, Rifadin® IV, Rimactane®) St. John's Wort	MODERATE INDUCERS	Bosentan (Tracleer®) Efavirenz (Sustiva®) Etravirine (Intelence®) Modafinil (Provigil®) Nafcillin (Unipen, Nallpen®)
STRONG INHIBITORS	Boceprevir (Victrelis®) Clarithromycin (Biaxin®) Cobicistat (part of Stribild®) Conivaptan (Vaprisol®) Fluvoxamine (Luvox®) Grapefruit juice a Indinavir (Crixivan®) Itraconazole (Sporanox®) Ketoconazole (Nizoral®) Lopinavir and Ritonavir (Kaletra®) Mibepradil (Posicor®) Nefazodone (Serzone®) Nelfinavir (Viracept®) Posaconazole (Noxafil®) Quinupristin (Synercid®) Ritonavir (Norvir®, part of Viektira Pak™) Saquinavir (Invirase®) Telaprevir (Incivek®) Telithromycin (Ketek®) Voriconazole (Vfend®)	MODERATE INHIBITORS	Amprenavir (Agenerase®) Aprepitant (Emend®) Atazanavir (Reyataz®) Ciprofloxacin (Cipro®) Darunavir/ritonavir (Prezista®/Ritonavir) Diltiazem Erythromycin Fluconazole (Diflucan®) Fosamprenavir (Lexiva®) Grapefruit juice a Imatinib (Gleevec®) Verapamil (Calan®)

a The effect of grapefruit juice varies widely among brands and is concentration-, dose-, and preparation-dependent. Studies have shown that it can be classified as a “strong CYP3A inhibitor” when a certain preparation was used (e.g., high dose, double strength) or as a “moderate CYP3A inhibitor” when another preparation was used (e.g., low dose, single strength). (FDA Drug Development and Drug Interactions <http://www.fda.gov/Drugs/DevelopmentApprovalProcess/DevelopmentResources/DrugInteractionsLabeling/ucm093664.htm#classInhibit>).

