(including postural), headache, and somnolence (drowsiness). Common GI disturbances included dyspepsia, nausea, constipation, and vomiting; severe nausea and vomiting were dose limiting in a few cases. Reported psychiatric conditions included such events as agitation, insomnia, and confusional state. In controlled studies of pimavanserin in subjects with PDP, the most frequent TEAEs experienced by subjects in the pimavanserin 34 mg group compared with the placebo group were urinary tract infection (UTI) (7.4% pimavanserin 34 mg vs. 6.9% placebo), nausea (6.9% pimavanserin 34 mg vs. 4.3% placebo), peripheral edema (6.9% pimavanserin 34 mg, 2.2% placebo), fall (6.4% pimavanserin 34 mg vs. 9.1% placebo), and confusional state (5.9% pimavanserin 34 mg vs. 2.6% placebo). In the long-term open-label studies in subjects with PDP, the most frequent adverse events (AEs) include fall (29.3%), UTI (18.5%), hallucination (14.5%), decreased weight (12.4%), and confusional state (11.0%). It is difficult to interpret these incidence rates in the absence of a concurrent control group, but the overall incidence appears within what would be expected in subjects with the underlying neurodegenerative disease, psychosis, and advanced age.

Clinical and non-clinical safety pharmacology studies of pimavanserin suggest a potential risk for QT prolongation. The magnitude of effect in humans has been assessed in a thorough QT study with doses of pimavanserin ranging from 17 to 68 mg and in the Phase 3 PDP program with a clinical dose of 34 mg. An average prolongation of approximately 5-8 milliseconds (ms) was observed. No clinically significant patterns have been observed in serious adverse events (SAEs) and there has been no evidence of pimavanserin-related laboratory abnormalities. As of 30 October 2015, 67 subjects have died during study participation with the majority of deaths considered not related or unlikely related to study drug. Five of these deaths occurred in 6-week double-blind studies (1 subject received placebo, 1 subject received 10 mg pimavanserin, and 3 subjects received 34 mg pimavanserin), and 62 deaths occurred in the multi-year, long-term open-label extension studies where the majority of subjects have been treated with pimavanserin for greater than 2 years.

Additional information is provided in the Investigator's Brochure.

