## **5.7 Prior and Concomitant Medications**

All medications used up to 12 weeks prior to Baseline (Day 1) through Visit 6 (telephone visit) or ET are to be recorded.

In order to ensure that appropriate concomitant therapy is administered, it is essential that subjects be instructed not to take any medication without prior consultation with the Investigator (unless the subject is receiving treatment for a medical emergency).

The Investigator may prescribe, adjust, or discontinue appropriate medication to treat or manage AEs. The Sponsor and Investigator, or designee, will confer to determine whether it is appropriate to continue such a subject in the trial if a prohibited medication is prescribed.

Subjects who take prohibited concomitant medications during the trial will be discontinued, unless the discontinuation presents an unacceptable medical risk. The justification to allow the subject to continue in the trial will be made by the Sponsor with medical input from the Investigator, and will be documented. If allowed to remain in the trial, this will be reported as a major protocol deviation and not a waiver.

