### **5.7.2 Prohibited and Restricted Medications**

Restrictions for concomitant medications should be followed between the initial screening visit and the Week 12 (EOS/ET) visit as specified in [Appendix C](#) and [Appendix D](#). These appendices do not constitute an exhaustive list and any questions regarding prohibited and restricted medications should be discussed with the Medical Monitor or appropriate designee.

Use of medications that could interfere with study conduct or any questions regarding prohibited and restricted concomitant medications should be reviewed and/or discussed with the Medical Monitor or appropriate designee.

Medications that can prolong QT interval are prohibited (or restricted if approved by the Medical Monitor) as specified in Appendix C.

Treatment with an antipsychotic medication must be discontinued 2 weeks or at least 5 half-lives (whichever is longer) prior to the Baseline (Day 1) visit.

If a subject is on a medication prohibited by the protocol, the medication should be discontinued only if it is determined by the Investigator to be clinically appropriate (e.g., if the subject's symptoms are not well-controlled or if the subject cannot tolerate the current medication).

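### Appendix D's permission for moderate CYP3A4 inhibitors covers erythromycin, which Appendix C item 6 bars throughout the study as a QT-prolonging drug

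*Protocol*

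**What the plan says.** Appendix D sorts drugs by their effect on CYP3A4. Strong inhibitors and inducers must stop 1 week before study drug and are barred throughout. For the rest it says "Moderate inhibitors and inducers of CYP3A4 are allowed but should be used with caution". The moderate-inhibitor column includes the run "Diltiazem Erythromycin Fluconazole (Diflucan", with no footnote on erythromycin and no pointer to Appendix C.

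Appendix C item 6 deals with drugs that can prolong QT. Its first sub-list, of drugs barred for the duration of the study, contains "Antimicrobial and antimalarial drugs; levofloxacin, moxifloxacin, erythromycin, clarithromycin, and pentamidine".

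Section 5.7.2 applies both appendices from screening to Week 12 and adds: "Medications that can prolong QT interval are prohibited (or restricted if approved by the Medical Monitor) as specified in Appendix C".

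Section 5.7 gives the consequence of using a barred drug: "Subjects who take prohibited concomitant medications during the trial will be discontinued, unless the discontinuation presents an unacceptable medical risk". For a subject who is kept in, Appendix C says: "If allowed to remain in the trial, this will be reported as a major protocol deviation and not a waiver".

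**The concern.** The two appendices give opposite answers for one named antibiotic, and the one that permits it is laid out as a lookup table. A prescriber who thinks of erythromycin as an interaction question would go to Appendix D, find it in the permitted column and have no reason to look further.

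Antibiotic use is foreseeable in this population. Appendix C item 6 itself expects urinary and respiratory infections to be treated during the study. Section 1.2 reports urinary tract infection in 7.4% of subjects on pimavanserin 34 mg in the controlled Parkinson's disease psychosis studies, against 6.9% on placebo.

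The stake is safety and conduct. By the protocol's own classification, erythromycin can prolong QT and also inhibits the enzyme that metabolises pimavanserin. Of pimavanserin itself, section 1.2 says: "An average prolongation of approximately 5-8 milliseconds (ms) was observed". Section 6.2.5 schedules post-baseline ECGs only at Weeks 4 and 12, so a short course between those visits could pass without one.

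**Working it through.** The plan states no figure on this point, so the check is a name-by-name comparison followed by a date calculation.

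**Size of the lists**
- Appendix C item 6, barred for the duration: 15 antiarrhythmics + 5 antimicrobials and antimalarials + 2 others (methadone, cocaine) = 22.
- Appendix D, moderate agents: 12 inhibitors + 5 inducers = 17.
- Appendix D, strong inhibitors: 20.

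**Match against the 22-drug list**
- Moderate agents: 1 of 17, erythromycin. Here the appendices disagree.
- Strong inhibitors: 1 of 20, clarithromycin (Appendix D: "Boceprevir (Victrelis®) Clarithromycin (Biaxin"). It is barred in both places, so the appendices agree.

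**Other Appendix D entries that Appendix C treats differently**

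| Drug | Appendix D | Appendix C | Still matters after randomization ended? |
|---|---|---|---|
| Erythromycin | Moderate inhibitor: permitted with caution | Item 6: barred for the duration | Yes, for anyone still on drug |
| Ciprofloxacin | Moderate inhibitor: permitted with caution | Item 6: barred at Baseline; afterwards may be permitted for a bacterial infection at the PI's discretion | Baseline bar: no. Later condition: yes |
| Fluvoxamine, nefazodone | Strong inhibitors: stop 1 week before study drug, then barred | Item 2: stop at least 3 weeks before Baseline, then barred | No: both bar use on treatment, and only the washout differs |

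**Which rule governs erythromycin.** Section 5.7.2 refers QT-prolonging drugs to Appendix C. It also mentions restriction with the Medical Monitor's approval, but Appendix C places erythromycin in the sub-list barred throughout, not among the drugs allowed under conditions. The answer is therefore settled: erythromycin is prohibited.

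**How long a correction can matter.** The inputs are last randomization on 2 November 2017 (section 3.1.2), protocol date 20 November 2017 (synopsis), and Week 12 on Day 85 with a 3-day window (schedule of assessments). I take Day 1 as the day of randomization.
- Last Week 12 visit: 2 November 2017 + 84 days = 25 January 2018, or 28 January 2018 with the 3-day window.
- Time left from the protocol date: 10 days in November + 31 in December + 25 in January = 66 days, or 69 with the window.
- Earliest Day 1 still on drug at the protocol date: 20 November − 84 days = 28 August 2017, or − 87 days = 25 August 2017.

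The documents do not say how many of the 111 randomized subjects started on or after those dates, or whether anyone took erythromycin.

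**The case against.** The best defence is that the two appendices are cumulative. Appendix D is about metabolism only. Its reasoning, a roughly 3-fold rise in exposure with strong inhibitors, concerns nothing else. On that reading its permission means only that a drug is not barred on CYP3A4 grounds, and the drug must still clear Appendix C. Section 5.7.2 and exclusion criterion 6 cite the two appendices together. Appendix D describes itself as guidance and sends questions to the Medical Monitor. Section 5.7 tells subjects, emergencies aside, to take nothing without consulting the Investigator. A site that follows all of this makes no error.

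Most of this stands, and it keeps the point minor. It does not remove an unqualified permission from a table that never mentions Appendix C. The offer to consult the Medical Monitor helps only a site that sees a question, and a plain permission hides it.

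A reader might infer that the protocol leaves erythromycin's status open. It does not, because section 5.7.2 settles it. A reader might also infer that erythromycin is the only entry on which the appendices differ. That is true only for the list barred for the duration, as the table above shows.

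**Conclusion.** The point holds as a low-severity matter of conduct and safety. Appendix D's permission is wrong for one of its 17 moderate agents. Following it would expose a subject to a prohibited QT-prolonging drug and lead to discontinuation or a major deviation.

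Two larger conclusions are tempting and unsupported. One is that subjects were harmed or that the combined QT effect is large. The documents record no erythromycin use and give no exposure figure for moderate inhibitors, so no size can be put on a combined effect. The other is that the efficacy results are compromised. The point touches no endpoint, model or analysis-set definition, and the efficacy summaries are unaffected.

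The number of subjects affected is unknown and probably small. The window of 66 to 69 days assumes that the last subject's Day 1 was 2 November 2017 and that dosing ran to the Week 12 visit.

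**What to change.** **Now:** send sites a short clarification memo stating that erythromycin is prohibited under Appendix C item 6 and that ciprofloxacin may be used only as Appendix C allows. This restates rules already in force. It costs one memo to approximately 70 sites, with no new procedure, visit or data. To be useful it must go out while subjects are on drug, that is, before about 25 to 28 January 2018.

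**In any protocol amendment or notification:** make the whole of Appendix D subject to Appendix C, with the stricter rule applying, and mark erythromycin as prohibited. The general clause also resolves ciprofloxacin, fluvoxamine and nefazodone without separate edits.

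The text change is small, but section 10.5 requires it to go to the IRB/EC. If it is filed as an amendment, approval must be awaited unless one of that section's exceptions applies; a notification needs no approval. With so little dosing time left, the memo is the step that can still protect subjects, and the edit may not justify a submission of its own.
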